13.8 Interim Analysis

An interim analysis for futility when the first $n_1=33$ patients have completed 6-months of follow-up post-chemoradiation; that is, when the first $n_1=33$ patients are evaluable for the primary endpoint. If the estimated COR is greater than or equal to 0.8, then the study will stop early for futility. Otherwise, the study will continue and enroll and additional $n_2=66$ patients. Additionally, at this time the safety profile of the treatment arms may be evaluated and considered in the decision for study continuation.

If the true COR is = 1.0 (no improvement in the nintedanib arm), then there is a 59.0% chance of stopping early for futility. If the true COR is 0.26, then there is only a 10.6% chance of stopping early for futility.

15 ETHICAL AND REGULATORY STANDARDS

15.1 Ethical Principles

This study will not be initiated until the protocol and informed consent document(s) have been reviewed and approved by a properly constituted Institutional Review Board (IRB) or Independent Ethics Committee (IEC). Each participant (or legal guardian) shall read, understand, and sign an instrument of informed consent prior to performance of any study-specific procedure. It is the responsibility of the investigator to ensure that the participant is made aware of the investigational nature of the treatment and that informed consent is given.

The Investigator is responsible for the retention of the participant log and participant records; although personal information may be reviewed by authorized persons, that information will be treated as strictly confidential and will not be made publicly available. The investigator is also responsible for obtaining participant authorization to access medical records and other applicable study specific information according to Health Insurance Portability and Accountability Act regulations (where applicable).

This study will be conducted in compliance with all applicable laws and regulations of the state and/or country and institution where the participant is treated, in accordance with the Declaration of Helsinki, Good Clinical Practice, and according to the guidelines in this protocol, including attached appendices.

15.2 Informed Consent

The Investigator (or IRB specified designee) is responsible for obtaining written consent from each participant or the participant's legally authorized representative in accordance with ICH-GCP guidelines using the approved informed consent form, before any study specific procedures (including screening procedures) are performed. The informed consent form acknowledges all information that must be given to the participant according to ICH-GCP, including the purpose and nature of the study, the expected efficacy and possible side effects of the treatment(s), and specifying that refusal to participate will not influence further options for therapy. Any additional information that is applicable to the study must also be included. Additional national or institutionally mandated requirements for informed consent must also be adhered to. The participant should also be made aware that by signing the consent form, processing of sensitive clinical trial data and transfer to other institutions as needed for further processing is allowed.

The Investigator shall provide a copy of the signed consent form to the participant and the signed original shall be maintained in the Investigator File. A copy of the signed consent form must be filed in the participant file. At any stage, the participant may withdraw from the study and such a decision will not affect any further treatment options.

16 STUDY RESPONSIBILITIES

16.1 Data Collection

Data entry into the database is to be completed in a timely fashion (within 30 days) after the participant's clinic visit. If an AE is considered serious it is captured on both the Adverse Event page and the Serious Adverse Event Source Form, which is handled in an expedited fashion.

Data management activities will be performed using eClinical. eClinical is a suite of software tools that enables the collection, cleaning and viewing of clinical trial data. CRS data management will design the study-specific database and facilitate its development by the eClinical Information Technology team. Once the database design is approved by the Investigator, Statistician, and Clinical Research Coordinator, the database will be put into production and data entry can begin. Data can be entered and changed only by those with the rights to do so into the eCRFs (via the EXPeRT Module). eClinical is compliant with all relevant technical aspects of relevant GCP guidelines.

- The system can generate accurate copies of stored data and audit trail information in human readable form.
- System access is limited to authorized individuals through the controlled assignment of unique ID and password combinations.
- The system is designed to periodically force users to change their passwords and verifies that user ID and password combinations remain unique.
- The system automatically generates a permanent time-stamped audit trail of all user interactions.

When data entry is complete, data management will review the data and will query any missing, incomplete, or invalid data points for resolution by the Clinical Research Coordinator and Investigator. Once all queries have been resolved, the data can be released to the statistician for analysis.

16.2 Maintenance of Study Documents

Essential documents will be retained per RPCI's policy for 6 years from the study termination date. These documents could be retained for a longer period, however, if required by the applicable local regulatory requirements or by an agreement with RPCI.

17 ADMINISTRATIVE RULES

17.1 Revisions to the Protocol

RPCI may make such changes to the protocol as it deems necessary for safety reasons or as may be required by the U.S. FDA or other regulatory agencies. Revisions will be submitted to the IRB/ERC for written approval before implementation. Approval must be obtained of any amendments prior to implementation at each participating institution from their respective IRBs.

17.2 Termination of the Study

It is agreed that, for reasonable cause, either the RPCI Investigators or NCCN, may terminate this study, provided a written notice is submitted within the time period provided for in the Clinical Trial Agreement. In addition, RPCI may terminate the study at any time upon immediate notice if it believes termination is necessary for the safety of participants enrolled in the study.

17.3 Confidentiality

Any data, specimens, forms, reports, video recordings, and other records that leave the site will be identified only by a participant identification number (Participant ID, PID) to maintain confidentiality. All records will be kept in a limited access environment. All computer entry and networking programs will be done using PIDs only. Information will not be released without written authorization of the participant.

2. INFORMED CONSENT

- Informed consent must be obtained by the **site Investigator/designee** from any participants wishing to participate, **prior to any procedures or treatment**.
- An informed consent template is provided by RPCI and can be amended to reflect institutional requirements.
- All consent changes **must** be reviewed by RPCI Network Office prior to submission to the site IRB.
- The informed consent must be IRB approved.
- Always check that the most up to date version of the IRB approved consent is being used.
- Within 5 business days, notify the RPCI Network Office of all participant withdrawals or consent to limited study participation and appropriately document the discontinuation and the reason(s) why.

3. PARTICIPANT REGISTRATION

The participant completes the Gender, Race, and Ethnicity Form and this is placed in the study binder.

RPCI does not grant exceptions to eligibility criteria.

Phase 1 Protocol Registration Instructions

Contact the RPCI Network Monitor to verify that a slot is available in the open cohort when a participant has been identified. **Do not have the participant sign consent prior to verifying an open slot.**

- After the participant signs consent, the Subject Screening and Enrollment Log must be faxed or emailed to the RPCI Network Monitor within 1 business day. The RPCI Network Monitor

will confirm receipt of the Subject Screening and Enrollment Log and email the participant ID number.

- When the participant has met eligibility, a signed eligibility checklist and other requested documentation will be faxed or emailed to the RPCI Network Monitor.
- Within 1 business day of receipt of the eligibility check list, the RPCI Network Monitor will fax or email the cohort assignment and dose level.
- An email must be sent by the site to confirm receipt of the cohort assignment and to provide the planned treatment start date.

Phase 2 Protocol Registration Instructions

The Subject Screening and Enrollment Log must be faxed or emailed to the RPCI Network Office within 1 business day of the date the participant is consented. Once the Investigator has determined that eligibility has been met, complete the eligibility check list and fax or email it to the RPCI Network Monitor at [contact].

4. STUDY DEVIATIONS

- If a deviation has occurred to eliminate hazard, this must be reported to the RPCI Network, site IRB and any other regulatory authority involved in the study.
- ALL study deviation will be recorded on the **Study Deviation Log**.
- Participants inadvertently enrolled with significant deviation(s) from the study-specified criteria will be removed from the study, at the discretion of the Principle Investigator.

5. STUDY DOCUMENTATION

- Study documents must be filled out completely and correctly. Ditto marks are not allowed.
- If an entry has been documented in error put a single line through the entry and initial and date the change. The RPCI Network Monitor must be able to read what has been deleted.
- Do **NOT** use white-out, magic marker, scratch-outs.
- Do **NOT** erase entries.
- Use only black ink for documentation on the accountability form and any other study forms.
- It is the responsibility of RPCI to inform the Investigator/ institution as to when these documents no longer need to be retained. If, for any reason, the Investigator desires to no longer maintain the study records, they may be transferred to another institution, another investigator, or to RPCI upon written agreement between the Investigator and RPCI.

6. **DRUG ACCOUNTABILITY**

Drug accountability must be strictly maintained.

- Responsibility rests solely with the Investigator but can be delegated as appropriate (e.g., to pharmacy personnel).
- A drug accountability record form (DARF) will record quantities of study drug received, dispensed to participants and wasted, lot number, date dispensed, participant ID number and initials, quantity returned, balance remaining, manufacturer, expiration date, and the initials of the person dispensing the medication.
- Study drug supply will only be used in accordance with the IRB approved study.
- Drug accountability forms are protocol and agent specific, they are study source documents and will be used to verify compliance with the study.
- An inventory count must be performed with each transaction. Any discrepancies shall be documented and explained.
- Drug accountability forms must be stored with study related documents.
- Each medication provided for this study and each dosage form and strength must have its own DARF.
- Dispensing the wrong study supply is considered a **medication error**.
- **NEVER** replace investigational agents with commercial product.
- Do **NOT** “transfer”, “borrow” or “replace” supplies between studies.

7. **SERIOUS ADVERSE EVENT REPORTING**

The site Investigator or designated research personnel will report all SAEs, whether related or unrelated to the investigational agent(s) to the **IRB in accordance with their local institutional guidelines**. The site will notify the RPCI Network Monitor within 1 business day of being made aware of the SAE. A preliminary written report must follow within 1 business day of the first notification using the following forms:

- RPCI SAE Source form
- MedWatch 3500A (modify as required per protocol)
- Refer to **Section 11.3** for details regarding SAE reporting to BI and NCCN.

A complete follow-up report must be sent to the RPCI Network Monitor when new information becomes available.

8. **UNANTICIPATED PROBLEM REPORTING**

An unanticipated problem (UP) is any incident, experience, or outcome that meets all of the criteria in **Section 11.5**.

For all adverse events occurring that are unanticipated and related or possibly related to the research drug, biologic or intervention, the participating physician or delegated research staff

from each site will notify their local **IRB in accordance with their local institutional guidelines**. The site must also notify the RPCI Network Monitor within 1 business day of being made aware of the Unanticipated Problem by completing the **RPCI Unanticipated Problem Report Form** and faxing or emailing it to the RPCI Network Monitor.

Appendix B. Procedures for the Follow-Up of a Potential Drug-Induced Liver Injury Case (Hy's Law Case)

Introduction

Drug-induced liver injury

Drug-induced liver injury (DILI) has been the most frequent single cause of safety-related drug marketing withdrawals for the past 50 years (e.g., iproniazid), continuing to the present (e.g., ticrynafen, benoxaprofen, bromfenac, troglitazone, nefazodone). Accordingly, detection of drug-induced liver injury of an investigational compound has become an important aspect of patient's safety guarding in drug development.

The US-FDA has published a Guidance for Industry entitled, "Drug-Induced Liver Injury: Premarketing Clinical Evaluation" which outlines the detection, evaluation, follow-up and reporting of drug-induced liver injury in clinical trials. Drugs that have the potential for inducing severe liver injury may be identified by marked peak aminotransferase elevations (10 - , 15 x ULN), or the combination of hepatocellular injury (aminotransferase elevation ≥ 3 x ULN) and altered liver function (hyperbilirubinemia ≥ 2 x ULN) which is defined as potential "Hy's law case" if not explained by other causes including evidence of biliary obstruction (i.e., significant elevation of alkaline phosphatase, ALP > 2 x ULN) or some other explanation of the injury (e.g., viral hepatitis, alcohol hepatitis, concomitant use of other known hepatotoxic drugs). This constellation predicts a poor outcome and although very rare, these potential cases have to be well characterized as soon as being identified as other confounding conditions may be the cause.

In further consideration of this FDA Guidance, any potential "Hy's Law case" has to be reported in an expedited manner to the FDA (i.e., even before all other possible causes of liver injury have been excluded) and be followed-up appropriately. The follow-up includes a detailed clinical evaluation and identification of possible alternative etiologies for the "Hy's Law case" constellation such as concomitant diseases (e.g., Hepatitis B) and/or other concomitant therapies that might potentially be hepatotoxic.

Although rare, a potential for drug-induced liver injury is under constant surveillance by sponsors and regulators. Therefore, this study requires timely detection, evaluation, and follow-up of laboratory alterations of selected liver laboratory parameters to ensure patients' safety.

The concept below has been worked out by Boehringer Ingelheim (BI) in order to guard patient's safety and to respond to regulatory requirements. It is the basis for all clinical studies and should be applied as appropriate.

Definition

The following changes in the laboratory values are considered to be a protocol-specific significant adverse event for all patients with normal values for ALT/AST at baseline:

- An elevation of ALT and / or AST > 5 x ULN without bilirubin elevation measured in the same blood draw sample.

- An elevation of AST and/or ALT > 2.5 fold ULN combined with an elevation of bilirubin to >1.5 fold ULN measured in the same blood draw sample.

These definitions are in line with the current dose reduction recommendations as outlined in all study protocols for nintedanib.

Patients showing these laboratory abnormalities need to be followed up until the protocol specific retreatment criteria have been met.

For patients with elevated ALT/AST values at baseline special considerations apply, if they are eligible for inclusion into the trial, e.g., if liver metastasis are present and do not qualify as exclusion criterion. For those special cases the BI contact person should be involved.

Procedures

Protocol-specified significant events are to be reported in an expedited manner similar as Serious Adverse Events, even if they do not meet any of the seriousness criteria and documented in the eCRF.

Replication of the following laboratory tests for confirmation within 48 hours:

- AST
- ALT
- bilirubin measurement (total and direct bilirubin)
- Alkaline Phosphatase
- Haptoglobin
- Complete blood count and cell morphology
- Reticulocyte count
- CK
- LDH

The results of these repeated laboratory tests must be documented on the eCRF /CRF forms and reported immediately via the SAE form to BI.

An evaluation of the patient within 48 hours with respect to but not limited to:

- Abdominal ultrasound or clinically appropriate other imaging and investigations adequate to rule out biliary tract, pancreatic, intra- or extrahepatic pathology, e.g., bile duct stones, neoplasm, hepatic tumor involvement, biliary tract, pancreatic or intrahepatic pathology, vascular hepatic conditions such as portal vein thrombosis or right heart failure. These data need to be collected, documented in the respective field of the eCRF/CRF/additional documentation form, and the respective SAE form has to be updated and forwarded to BI.
- Detailed history of current symptoms and concurrent diagnoses and medical history.
- Detailed history of concomitant drug use (including non-prescription medications, herbal and dietary supplement preparations and e.g., steroids as concomitant supportive

treatment), alcohol use, recreational drug use, and special diets detailed history of exposure to environmental chemical agents.

In case that both imaging and laboratory value did not unequivocally confirm cholestasis as the reason of ALT/AST increase, in particular if AP < 2 x ULN, then please complete the following laboratory tests:

- Clinical chemistry (i.e., alkaline phosphatase, cholinesterase (either plasma or red blood cell), albumin, PT or INR, CK, CK-MB, ceruloplasmin*, α -1 antitrypsin*, transferrin, ferritin, amylase*, lipase*, fasting glucose*, cholesterol, triglycerides)
- Serology (i.e., hepatitis A (Anti-IgM, Anti-IgG), hepatitis B (HbsAg, anti-HBs, DNA), hepatitis C (anti-HCV, RNA if anti-HCV positive), hepatitis D (anti-IgM, Anti-IgG)*, hepatitis E (anti-HEV, anti-HEV IgM, RNA if anti-HEV IgM positive)*, anti-smooth muscle antibody (titer)*, anti-nuclear antibody (titer)*, anti-LKM (liver-kidney microsomes) antibody*, anti-mitochondrial antibody*, Epstein Barr Virus (VCA IgG, VCA IgM), cytomegalovirus (IgG, IgM), herpes simplex virus (IgG, IgM), varicella (IgG, IgM), parvovirus (IgG, IgM))
- Hormones, tumor marker (i.e., TSH*)
- Hematology (i.e., thrombocytes*, eosinophils*)

*If clinically indicated and in case that additional investigations are needed (e.g., immunocompromised patients.)

Initiate close observation of all patients with elevated liver enzyme and bilirubin elevations by repeat testing of ALT, AST, bilirubin (with fractionation into total and direct) and AP at least weekly until the laboratory values return to normal or to the values as defined in the protocol.

In case that transaminases and/or bilirubin increase despite cessation of the experimental therapy, more frequent intervals will be warranted.

Depending on further laboratory changes, additional parameters identified e.g. by reflex testing will be followed up based on medical judgement and Good Clinical Practices

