6 PARTICIPANT SELECTION

6.1 Inclusion Criteria

- 1 Age 18 years or greater.
- 2 Histologically or cytologically-proven non squamous cell NSCLC. Mixed histology with SCLC component not allowed.
- 3 Patients with Stage II - IV non squamous cell NSCLC who received at least 54 Gy of total planned thoracic radiation dose will be eligible. Patients must have received at least one cycle of chemotherapy concurrently during the course of thoracic radiation. Regimens allowed are platinum combinations with either etoposide or a taxane regardless of histology subtype; platinum with pemetrexed for patients with nonsquamous NSCLC only. Patients with oligometastatic Stage IV cancer are eligible if they have received only one line of systemic therapy for their Stage IV cancer prior to the concurrent chemoradiation phase.
- 4 Patient must have had a CR/PR/SD, 4-6 weeks after completing last fraction of radiation therapy.
- 5 ECOG Performance Score 0 - 2 (**Appendix C**).
- 6 ANC $\geq 1,500/\mu\text{L}$.
- 7 Platelet count $\geq 100,000/\mu\text{L}$.
- 8 Hemoglobin ≥ 9 g/dL.
- 9 Total bilirubin \leq normal or for those with Gilbert's syndrome ≤ 1.5 times upper limit of normal (ULN) OR direct bilirubin normal (per institute standards).
- 10 AST $\leq 1.5 \times$ ULN. ALT and AST $\leq 2.5 \times$ ULN is acceptable if there is liver metastasis.
- 11 Fertile patients must use adequate contraception.

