7.2.1 Definition of DLTs for the Combination of Nintedanib with Durvalumab

A DLT is defined by the occurrence of toxicities outlined below attributable to either Nintedanib alone or the combination of Nintedanib plus durvalumab. Toxicity will be assessed using the NCI Common Toxicity Criteria for Adverse Events (CTCAE) version 4.03. DLTs must be scored as possibly, probably, or definitely related to either Nintedanib alone or the combination of Nintedanib plus durvalumab within the first 28 days of combination treatment. Patients who developed significant DLTs deemed possibly, probably or definitely related to Nintedanib (alone or in combination) will be taken off study.

- Nausea of CTCAE Grade ≥ 3 , despite maximal supportive care

- Vomiting of CTCAE Grade ≥ 3 , despite maximal supportive care
- Diarrhea of CTCAE Grade ≥ 3 of any duration despite maximal supportive care
- AST and/or ALT $> 5x$ ULN regardless of total bilirubin level
- AST and/or ALT $> 2.5x$ ULN together with total bilirubin $> 1.5x$ ULN (or $1.5x$ baseline in patients with Gilbert's syndrome)
- Other non-hematological adverse event of CTCAE Grade ≥ 3 considered drug-related and clinically significant (except transient electrolyte abnormality, alopecia, untreated vomiting or diarrhea, and isolated elevation of gamma glutamyl transpeptidase which will not be considered as DLT)
- CTCAE grade 4 Neutropenia and fever $\geq 38.5^{\circ}\text{C}$
- Neutropenia CTCAE Grade 4 for more than 7 days, without fever $> 38.5\text{ C}$
- Platelets CTC grade 4 or CTC grade 3 associated with bleeding or requiring transfusion
- Grade > 2 proteinuria
- Nintedanib $< 50\%$ of prescribed dose for the first cycle or inability to resume nintedanib dosing within 14 days of stopping due to treatment-related toxicity
- Durvalumab < 2 doses received

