7.3.2 Treatment Delay

Treatment delay of immune checkpoint inhibitor will follow standard practice in managing toxicities attributed to immune checkpoint inhibitor or for other reasons (scheduling preference, etc). No dose reductions are allowed.

Treatment with nintedanib/placebo has to be interrupted in case **ANY** of the criteria listed below is fulfilled.

- Nausea of CTCAE Grade ≥ 3 , despite supportive care
- Vomiting of CTCAE Grade ≥ 2 , despite supportive care
- Diarrhea of CTCAE Grade ≥ 2 for more than 3 consecutive days, despite supportive care
- AST and/or ALT of CTCAE Grade ≥ 2 in conjunction with bilirubin of CTCAE Grade ≥ 1
- AST and/or ALT of CTCAE Grade ≥ 3

- Other non-hematological adverse event of CTCAE Grade ≥ 3 considered drug-related
- Neutropenia and fever $> 38.5^{\circ}\text{C}$
- Neutropenia CTCAE Grade 4 for more than 7 days, without fever
- Platelets $< 25,000\text{mm}^3$, with or without bleeding
- Grade > 2 proteinuria

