11.3 Investigator Reporting: Notifying Boehringer Ingelheim

The following events are considered as Protocol-specified events of special interests:

Any gastrointestinal and non-gastrointestinal perforations, leakage, fistula formation, abscess.

In such case the following additional information need to be collected, documented in the respective comment field of the BI IIS SAE form and the respective narratives of the SAE. That has to be forwarded to Boehringer Ingelheim:

- Location of perforation, leakage, fistula, abscess

- Location/extent of abdominal tumor manifestations,
- Imaging and reports (CT, ultrasound, endoscopy, pathology, etc.)
- Prior surgery (location, wound healing complications)
- Concomitant diseases with GI involvement (e.g., M Crohn, vasculitis, tuberculosis, diverticulitis)
- Thromboembolic events (or predisposition)

Drug-induced liver injury is under constant surveillance by sponsors and regulators and is considered a protocol-specified adverse event of special interest (AESI). Timely detection, evaluation, and follow-up of laboratory alterations of selected liver laboratory parameters to distinguish an effect of the investigational drug from other causes are important for patient safety and for the medical and scientific interpretation of the finding.

The following are considered as protocol-specified AESI:

- An elevation of ALT and / or AST > 5 x ULN without bilirubin elevation measured in the same blood draw sample.
- An elevation of AST and/or ALT > 2.5 fold ULN combined with an elevation of bilirubin to > 1.5 fold ULN measured in the same blood draw sample.

Patients showing above laboratory abnormalities need to be followed up until the protocol specific retreatment criteria have been met and according to Appendix B of this clinical trial protocol.

Protocol-specified AESI are to be reported in an expedited manner similar to Serious Adverse Events, even if they do not meet any of the seriousness criteria.

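### Read literally, the two hepatic AESI triggers leave out ALT/AST above 5 x ULN when bilirubin is above ULN but not above 1.5 x ULN

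*Combined protocol and SAP*

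**What the plan says.** The two hepatic triggers appear with the same thresholds in Section 11.3 and in Appendix B under Definition.

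- Trigger 1: "An elevation of ALT and / or AST > 5 x ULN without bilirubin elevation measured in the same blood draw sample".
- Trigger 2: ALT and/or AST above 2.5 x ULN "combined with an elevation of bilirubin to >1.5 fold ULN measured in the same blood draw sample".

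Two consequences follow from meeting either one. Section 11.3 states that "Protocol-specified AESI are to be reported in an expedited manner similar to Serious Adverse Events", whether or not a seriousness criterion is met, and Appendix B repeats this. Appendix B, Procedures, adds a repeat laboratory panel and a patient evaluation, each within 48 hours. Appendix B limits its definition to patients with normal ALT/AST at baseline and says that its concept is to be applied as appropriate. Section 11.3 does not restrict its triggers by baseline enzymes.

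Three other places deal with the same laboratory picture:

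- Section 7.2.1 (Phase I DLTs) uses the same pair of cut-offs, but its first limb is AST and/or ALT above 5 x "ULN regardless of total bilirubin level".
- Section 7.3.2 (Phase II interruption) holds drug for AST/ALT of Grade 3 or more, and already at Grade 2 or more when it occurs "in conjunction with bilirubin of CTCAE Grade" 1 or more.
- Section 7.3.5, Table 4, reduces the dose for AST/ALT of Grade 3 or more with no bilirubin condition. Appendix B says of its own triggers: "These definitions are in line with the current dose reduction recommendations as outlined in all study protocols for nintedanib".

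**The concern.** Trigger 1 excludes any bilirubin elevation and gives no threshold for one. Trigger 2 starts only above 1.5 x ULN. Between the two lies a band in which bilirubin is raised, so trigger 1 fails, but not raised enough for trigger 2. A patient with ALT at 6 x ULN and normal bilirubin must be reported. If bilirubin is 1.3 x ULN, a worse picture, the requirement lapses. At 1.6 x ULN it returns. Section 7.3.2 works the other way: there a raised bilirubin lowers the enzyme grade needed for action.

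The band has no upper enzyme limit. It therefore includes the 10 to 15 x ULN range, and Appendix B's introduction says that drugs with potential for severe liver injury "may be identified by marked peak aminotransferase elevations" of that size.

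At stake are the prompt work-up and the completeness of expedited reports to the manufacturer for a toxicity that Section 1.4.1 describes as the main dose-limiting one for nintedanib. The primary and secondary efficacy analyses are not touched.

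**Working it through.** The plan gives no figure to reproduce, so this is a check of logic. Let A be ALT or AST, and B total bilirubin, both in multiples of ULN and from the same sample.

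**Inputs**

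- Trigger 1, literal (11.3, Appendix B): A > 5 and B ≤ 1.
- Trigger 2 (11.3, Appendix B): A > 2.5 and B > 1.5.
- DLT laboratory rule (7.2.1): A > 5 at any B, or A > 2.5 and B > 1.5.
- Potential Hy's law case (Appendix B, Introduction): A ≥ 3 and B ≥ 2.

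**Step 1: what the triggers cover when A > 5.** Trigger 1 covers B ≤ 1 and trigger 2 covers B > 1.5. What remains is 1 < B ≤ 1.5. The results at A = 6, 10 or 15 are identical:

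| B (x ULN) | Trigger 1, literal | Trigger 2 | AESI as written | AESI with DLT wording |
|---|---|---|---|---|
| 1.0 | met | not met | yes | yes |
| 1.1 | not met | not met | **no** | yes |
| 1.3 | not met | not met | **no** | yes |
| 1.5 | not met | not met | **no** | yes |
| 1.6 | not met | met | yes | yes |
| 2.0 | not met | met | yes | yes |

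**Step 2: comparison with the DLT rule.** Trigger 2 equals the second limb of the DLT rule. The first limbs differ only in the bilirubin condition. The DLT rule therefore exceeds the two triggers by exactly A > 5 with 1 < B ≤ 1.5. The protocol thus already has a version of these cut-offs with no gap.

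**Step 3: Hy's law.** If A ≥ 3 and B ≥ 2, then A > 2.5 and B > 1.5, so trigger 2 is always met. No result at that level is missed.

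**Step 4: the looser reading.** If trigger 1 means A > 5 and B ≤ 1.5, then together with trigger 2 every A > 5 is covered and the band disappears.

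**Step 5: effect of the fix.** With trigger 1 as A > 5 at any B, every result that now meets a trigger still does, because A > 5 with B ≤ 1 is contained in A > 5. The band is added and nothing is lost.

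**Step 6: what still applies in the band.**

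- Phase II: interruption (7.3.2) and dose reduction (7.3.5), assuming that Grade 3 AST/ALT starts above 5 x ULN. The documents do not print that cut-off.
- Phase I: a DLT if at least possibly related to nintedanib, alone or with durvalumab, within the first 28 days (7.2.1).
- Recording as an adverse event if clinically significant and needing active management (11.1.1.3).
- SAE reporting if judged an important medical event (11.2.1).
- Re-testing at least weekly: the Appendix B sentence, taken at its word, covers patients with both enzymes and bilirubin raised.

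None of these in itself requires the 48-hour panel, the 48-hour evaluation or the AESI report.

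**The case against.** The strongest reply is that the gap depends on an undefined phrase. The two triggers are a pair, and the only bilirubin elevation quantified in the pair is the one above 1.5 x ULN. On that view trigger 1 means without that elevation, and no band is left. The gap-free DLT list and Appendix B's statement that its definitions match the dose-reduction recommendations then show how the authors meant trigger 1 to be read.

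Much of this stands as evidence of intent, and the gap is probably a wording slip. It does not settle what sites will do. Where 1.5-fold was meant, the text says so in trigger 2; in trigger 1 it does not. A reporting trigger should not need to be inferred from another section.

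The second reply is that the work-up is not a strict mandate. Appendix B is to be applied as appropriate, Section 7.4.4 points to it for guidelines, and Appendix B also says the study requires timely detection, evaluation and follow-up of liver laboratory changes. This stands. An investigator may well do the 48-hour work-up in the band; the point is only that the definition does not call for it. For patients with raised baseline ALT/AST, Appendix B's definition does not apply in any case.

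The third reply, that the safeguards in step 6 limit the harm, also stands. One reservation: the weekly re-testing sentence sits among the procedures for triggered events, so its reach into the band can be argued either way.

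**Conclusion.** The point holds as a minor defect of wording in a safety-reporting definition, conditional on the literal reading in which any bilirubin above ULN is an elevation. On that reading the uncovered band is exactly ALT/AST above 5 x ULN with bilirubin above ULN and up to 1.5 x ULN. What lapses there is the expedited AESI report and, for patients with normal baseline ALT/AST, the Appendix B 48-hour tests and evaluation.

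The number of patients cannot be derived. Section 1.4.2 says that enzyme rises on nintedanib monotherapy came with raised bilirubin in only a few cases, so few are expected. No corresponding figure is given for the durvalumab combination.

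A reader might infer that patients in the band are left without protection, or that dangerous cases escape altogether. The documents do not support that. The dosing rules, DLT rules, adverse event recording and the SAE route remain, and every result at the Hy's law level meets trigger 2. Nor do they support calling the 48-hour work-up an absolute requirement that is withdrawn in the band, given the latitude Appendix B allows. Efficacy conclusions are unaffected.

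**What to change.** In trigger 1, in both Section 11.3 and Appendix B, delete the condition on bilirubin and use the DLT wording from Section 7.2.1, so that it reads ALT and/or AST > 5 x "ULN regardless of total bilirubin level". Leave trigger 2 as it is. Stating in trigger 1 that bilirubin is not above 1.5 x ULN would have the same effect, but the DLT wording is already in the protocol and keeps the two lists aligned.

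The edit is one phrase in each of two places. It adds a few expedited reports, repeat panels and evaluations. Appendix B says the manufacturer worked out the concept, so its agreement to the wording is probably needed.
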